CPAP	Continuous Positive Airway Pressure
CRF	Case Report Form
EC	Ethics Committee
EEG	Electroencephalography
IB	Investigator's Brochure
ICH	International Council for Harmonisation of Technical Requirements for Pharmaceuticals for Human Use
eCRF	Electronic Case Report Form
pCRF	Paper Case Report Form
GCP	Good Clinical Practice
GFAP	Glial Fibrillary Acidic Protein
HSAT	Home sleep apnea test
ICF	Informed Consent Form
MCI	Mild Cognitive Impairment
MOCA	Montreal Cognitive Assessment
MRI	Magnetic Resonance Imaging
ODI	Oxygen Desaturation Index
OSA	Obstructive Sleep Apnea
PET	Positron Emission Tomography
PHI	Personal Health Information
PI	Principal Investigator
PSG	Polysomnography
PVS	Perivascular Space
QI	Qualified Investigator
REB	Research Ethics Board
RCT	Randomized Controlled Trial

REM	Rapid Eye Movement
SAE	Serious Adverse Event/Serious Adverse Experience
SDMT	Symbol Digit Modalities Test
SOP	Standard Operating Procedure
SRI	Sunnybrook Research Institute
SUADR	Serious and Unexpected Adverse Drug Reaction
TMF	Trial Master File

PROTOCOL SUMMARY

Protocol Title (Short Title)	Treating Sleep Apnea to Improve Cognitive Function, Alzheimer's Disease Pathology, and Astrocyte Activation in Older Adults with Cognitive Impairment: A Multi-Centre Randomized Controlled Trial (CPAP Randomized Controlled Trial)
Protocol Number	CTO 5040
Phase	II
Study Design	Single-blinded randomized controlled trial
Study Duration	3 years
Setting	Community-dwelling older adults who respond to recruitment initiatives and advertisements, or patients attending dementia prevention clinics, memory clinics, or sleep clinics throughout the Greater Toronto Area
Sample Size	206 participants randomized to either: Early CPAP group: Brain Health Support PRO sleep modules (BHP-sleep; a web-based sleep education intervention) and Continuous Positive Airway Pressure (CPAP) for 8 months; or Later CPAP group: BHP-sleep for first 4 months, then BHP-sleep and CPAP for remaining 4 months of participation. Target sample size for each group is 103.
Main Inclusion Criteria	Older adults with mild cognitive impairment (MCI) and previously untreated obstructive sleep apnea (OSA)
Primary Outcome(s):	This trial tests the hypothesis that in older adults with MCI and previously untreated OSA, 4 months of web-based sleep education and CPAP will improve cognitive function more than web-based sleep education alone. This trial also tests the hypothesis that 8 months of CPAP will improve cognitive function more than 4 months of CPAP. The primary outcome of this study will be change in the Symbol Digit Modalities Test (SDMT). The SDMT is a test of speeded executive function that is predictive of clinically significant improvement in patients with MCI. Additional cognitive measures that supplement the primary outcome of this study will be: attention and executive function (Trail Making Test A & B), working memory (Digit Span and Letter-Number Sequencing), verbal learning and memory (Hopkins Verbal Learning Test), and severity of cognitive impairment (Alzheimer's Disease Assessment Scale – Cognitive Subscale; ADAS-Cog-13).

Secondary Outcome(s):	
This trial will also assess change in 1) Magnetic Resonance Image (MRI) quantified brain perivascular spaces (PVS) 2) plasma glial fibrillary acidic protein (GFAP) and 3) plasma pTau-181.
 
This trial will also aim to identify features of sleep physiology that mediate the impact of CPAP on cognitive function.
 
An exploratory subset of 28 participants (14 per group) will be invited to participate in a sub-study with its own protocol and informed consent process where changes in microglial activation will be assessed by [¹⁸F]FEPPA Positron Emission Tomography (PET).

Planned Treatment	
Early CPAP group: Participants randomized to this group will start BHP-sleep and CPAP simultaneously and continue both for 8 months. BHP-sleep consists of the sleep modules of the Canadian Consortium on Neurodegeneration in Aging's (CCNA) online Brain Health PRO platform covering sleep physiology, healthy sleep habits, and information about sleep disorders like sleep apnea. Participants will receive a study-provided auto-titrating CPAP device, with settings set by one of the study sleep medicine physicians according to current clinical practice parameters. Participants will undergo an in-person mask fitting, and then will be supported by a sleep technologist with extensive clinical experience with CPAP.
 
Later CPAP group: Participants randomized to this group will start BHP-sleep without CPAP for first 4 months, followed by BHP-sleep and CPAP simultaneously for remaining 4 months of participation.

Statistical Analysis:	
For our primary analysis, this trial will model performance on the SDMT as a function of time (baseline vs. 4 months) and study group (Early CPAP vs. Later CPAP). In secondary analyses, we will consider a series of models replacing the SDMT with our secondary cognitive endpoints.
 
We will repeat the analyses above, considering the change between baseline and 8 months. We will also conduct a mixed-effect analysis including both the 4-month and 8-month time points.
 
We will again repeat the analyses above, replacing our cognitive outcomes with a) plasma GFAP b) plasma pTau-181 and c) MRI PVS burden.
 
Finally, we will use mediation analysis to examine the extent to which the effect of CPAP on change in SDMT is mediated by specific changes in sleep physiology.

2 INTRODUCTION

This study document is the protocol for research involving human participants. This study is to be conducted according to Canadian and international standards, and in compliance with the protocol, the International Council for Harmonisation of Technical Requirements for Pharmaceuticals for Human Use (ICH) Good Clinical Practice E6 (GCP), World Medical Association Declaration of Helsinki: Ethical Principles for Medical Research Involving Human Participants, as well as applicable regulatory and institutional requirements and research policies.

2.1 Background

Sleep disruption and cognitive impairment frequently coexist. Several forms of sleep disruption, including sleep apnea (1), are associated with more rapid cognitive decline and Alzheimer's disease (AD) related brain changes. However, observational studies, particularly those in older adults, cannot determine whether sleep disruption contributes to or is a consequence of AD-related brain changes. Indeed, there has been a lack of randomized controlled trials (RCT) demonstrating an impact of any sleep intervention on cognitive decline or key AD-related brain changes.

Of particular interest is obstructive sleep apnea (OSA), a disorder characterized by repetitive obstruction of the upper airway in sleep leading to hypoxia, sleep fragmentation, and disrupted slow wave sleep. OSA is seen in up to 50% of patients with mild cognitive impairment (MCI) (Figure 1) and associated with more rapid cognitive decline (1). It is effectively treated by continuous positive airway pressure (CPAP); the application of positive airway pressure to splint open the upper airway preventing collapse. Observational studies suggest CPAP use is associated with improved cognitive function (Figure 2) and reduced perivascular space (PVS) burden (Figure 3).

This study will address residual knowledge gaps left by other observational studies of CPAP in MCI patients. The randomized design of this study will allow greater causal certainty than observational studies and may support a change in practice. This study may support screening for and treatment of OSA in individuals with MCI to improve cognition. There will be much deeper mechanistic dissection, particularly of microglial activation and perivascular biology (assessed using a neural network MRI segmentation tool we developed called SynthSegCSVD) (Figure 4). This will provide therapeutic targets for addressing the adverse effects of OSA on MCI-related outcomes in the individuals who cannot tolerate CPAP. This study will also use wearable sensors to assess the role of changes in sleep physiology in mediating the link between CPAP and MCI-related outcomes.

This study may provide evidence that for the ~50% of patients with MCI who have OSA, treatment with CPAP can improve cognition, and reduce key pathophysiological contributors to dementia including neurofibrillary tangle pathology (Figure 5), astrocyte (Figure 6) and microglial activation (Figure 7), and enlargement of perivascular spaces. This will support widespread treatment of OSA in patients with cognitive impairment to slow cognitive decline and reduce dementia-related brain changes. Moreover, it will identify the key sleep changes mediating these effects, which can then be specifically targeted by other interventions.

Our four key end users are 1) patients with MCI, sleep apnea, or both 2) sleep and dementia physicians who care for them 3) allied health practitioners supporting these patients and who would support CPAP adherence and 4) public health officials who would fund screening and treatment of sleep apnea.

2.2 Pre-Clinical and Clinical Data to Date

[figure not shown]

Figure 1: Sleep apnea is common in adults with MCI. We measured sleep apnea in 121 adults with MCI in the Memory and Aging Project using the WatchPAT wearable sensor. 61 participants (52%) had at least moderate sleep apnea.

[figure not shown]

Figure 2: CPAP improves hypoxia, sleep fragmentation and cognitive function in patients with sleep apnea. We treated 66 patients with newly diagnosed moderate sleep apnea (AHI>15; Apnea hypopnea index) with 4 months of CPAP. We measured oxygen saturation with pulse oximetry. We measured sleep fragmentation with 10 days of wrist actigraphy. Cognition was measured with the Toronto Cognitive Assessment. 4 months of CPAP was associated with dramatically reduced hypoxia (time with SpO₂<90%, panel A) and sleep fragmentation (kRA, panel B), and improved delayed memory performance (panel C).

[figure not shown]

Figure 3: CPAP use stabilizes MRI-visible perivascular space volumes. We treated 66 patients with newly diagnosed moderate (AHI>15) sleep apnea with 4 months of CPAP. We measured MRI-visible perivascular space volumes, which are thought to be a key contributor to cognitive impairment. ~50% of participants used CPAP >4 hours a day. In those not adherent with CPAP, PVS volumes increased over 4 months. However, CPAP adherence was associated with stabilisation of PVS volumes.

[figure not shown]

Figure 4: SynthSegCSVD, a new Convolutional Neural Network-Based Tool for Segmentation of Perivascular Spaces. We have developed and validated SynthSegCSVD for rapid automated segmentation of PVS from heterogeneous MRI datasets. This panel shows example SynthSegCSVD output showing PVS segmentation.

[figure not shown]

Figure 5: Better sleep consolidation is associated with lower neurofibrillary tangle density in genetically at risk adults. (interaction estimate, -0.42 ; SE, -0.17 ; $P= .02$) (2).

[figure not shown]
[figure not shown]

Figure 6: More consolidated (less fragmented) sleep is associated with lower expression of plasma glial fibrillary acidic protein (GFAP), a marker of astrocyte activation. In 415 older adults, we assessed gene expression in the dorsolateral prefrontal cortex by RNAseq and related this to sleep consolidation assessed by wrist accelerometry. Better sleep consolidation (lower sleep fragmentation) was associated with lower expression of GFAP.

2.3 Anticipated Benefits and Rationale

This study will provide class I evidence that CPAP, in combination with an online sleep optimization program, will improve memory and concentration, reduce Alzheimer's associated proteins, prevent brain blood vessel damage, and reduce brain inflammation, in adults with OSA and MCI. This will suggest that large scale screening for and treatment of OSA may be an effective means of preventing and potentially improve dementia-related outcomes. Moreover, it would be the first proof that improving sleep can in principle prevent dementia and open the door to trials of other interventions to improve sleep to prevent dementia.

3 STUDY OBJECTIVES

The overall goal of this randomized controlled trial is to test the hypothesis that in older adults with MCI and previously untreated OSA, 4 months of web-based sleep education and CPAP will improve cognitive function more than web-based sleep education alone. Secondarily, this trial will test the hypothesis that 8 months of CPAP will improve cognitive function more than 4 months of CPAP. Moreover this trial will test several mechanistic hypotheses, namely that 4 months of CPAP will 1) stabilize the growth of MRI-quantified brain perivascular spaces, a key correlate of cognitive impairment, 2) reduce plasma glial fibrillary acidic protein, a marker of astrocyte activation, 3) reduce plasma pTau-181, a marker of neurofibrillary tangle pathology – one of the pathological hallmarks of Alzheimer’s disease, and 4) identify features of sleep physiology that mediate the impact of CPAP on cognitive function.

An exploratory subset of 28 participants (14 per group) will be invited to participate in a sub-study with its own protocol and informed consent process aimed to assess change in microglial activation assessed by [¹⁸F]FEPPA Positron Emission Tomography (PET).

3.1 Primary Objective

The specific primary objectives are:

(1) Cognitive Function: Test the hypothesis that in adults with MCI and previously untreated moderate-severe OSA, 4 months of web-based sleep education and CPAP will improve cognitive function (or slow cognitive decline) as measured by the Symbol Digit Modalities Test (SDMT) more than web-based sleep education alone.

(2) Treatment Duration: Test the hypothesis that 8 months of CPAP will improve cognitive function (or slow cognitive decline) as measured by SDMT more than 4 months.

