9.2 Sample Size Considerations

Our primary outcome measure is the total score on the Symbol Digit Modalities Test (SDMT), a, a test of speeded executive function, at 4 months. A recent study estimated a minimal clinically important difference in the SDMT in a sample of adults with MCI of -3.8 points, corresponding to an effect size of -0.42 (2). An observational study of CPAP in adults with MCI found a similar effect size of CPAP (6-month effect size 0.46) on a very similar test, the Digit Symbol Substitution Test subtest of the Wechsler Adult Intelligence Scale (3). The test-retest correlation for the SDMT in clinically stable individuals with MCI over a mean follow-up of 19 months is 0.78 (2). In a recent study of adults with MCI, overall CPAP adherence was ~70% (10). In order to account for this, we will design our study to detect a smaller effect size of 0.26. Assuming a test-retest correlation of 0.78, and a 2-tailed type I error rate of 0.05 in a 2-group ANCOVA model, we estimate that a total sample size of 184 will provide 80% power to detect an effect estimate of 0.26. To account for an estimated 10% drop out, we will aim to recruit a total sample size of 206 participants (103 per group).

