9.4 Final Analysis Plan

Our primary analysis will be an intent-to-treat (ITT) analysis comparing difference on the SDMT at 4 months as a function of assigned treatment group (CPAP vs. web education alone), adjusted for baseline SDMT. The analysis will use linear regression, adjusted for baseline SDMT, age, sex, years of education and recruitment source (direct from community vs. hospital/clinic). Participants will be analyzed in the treatment group to which they were assigned irrespective of their actual treatment adherence. Intention to treat analyses preserve the benefits afforded by randomization (most importantly, the elimination of selection bias in treatment assignment), and are conservative in their estimates of treatment effect. As a secondary analysis, we will carry out a “per protocol” analysis where participants will be classified based on actual CPAP usage with participants considered CPAP users if they used CPAP >4h per night >80% of days over the preceding four months, and non-users if less than that.

Further analysis will be an intent-to-treat analysis comparing difference on the SDMT at 8 months, adjusted for baseline SDMT, as a function of assigned treatment group (CPAP 4 months vs. CPAP 8 months). The analysis will use linear regression, adjusted for baseline SDMT, age, sex, years of education and recruitment source (direct from community vs. memory clinic). As a secondary analysis, we will carry out a “per protocol” analysis where participants will be classified based on actual CPAP usage with participants considered CPAP users if they used CPAP >4h per night >80% of days in the four months leading up to cognitive evaluation.

We plan to repeat our initial analyses replacing our cognitive outcomes with a) plasma GFAP b) plasma pTau-181 and c) MRI PVS burden.

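### The 8-month comparison is primary in section 3.1 but not in sections 3, 9.2 or 9.4, and the 0.26 planning effect fits 62% adherence rather than the 70% cited for it

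*Protocol*

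**What the plan says.** **Rank of the 8-month comparison.** Section 3.1 lists two primary objectives. The first is the 4-month comparison on the SDMT. The second begins "Treatment Duration: Test the hypothesis that 8 months of CPAP will improve cognitive function" and compares 8 with 4 months of CPAP on the same test. Numbering of the secondary objectives in 3.2 starts at (3), so the placement looks deliberate. The Primary Outcome(s) entry of the protocol summary adds: "This trial also tests the hypothesis that 8 months of CPAP will improve cognitive function more than 4 months of CPAP".

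Other places rank it lower:

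- Section 3: "Secondarily, this trial will test the hypothesis that 8 months of CPAP will improve cognitive function more than 4 months of CPAP".
- Section 9.2 places the primary outcome at 4 months and sizes one two-sided test at 0.05.
- Section 9.4: "Our primary analysis will be an intent-to-treat (ITT) analysis comparing difference on the SDMT at 4 months". For the later visit: "Further analysis will be an intent-to-treat analysis comparing difference on the SDMT at 8 months".
- The summary's Statistical Analysis entry limits the primary analysis to baseline versus 4 months, then says: "We will repeat the analyses above, considering the change between baseline and 8 months".

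**Planning effect.** Section 9.2 takes 3.8 SDMT points (effect size 0.42) as the minimal clinically important difference. It cites a study with CPAP adherence of about 70% and continues: "In order to account for this, we will design our study to detect a smaller effect size of 0.26". From 0.26 it derives 184 participants, and 206 after 10% drop-out. Section 5.3 gives the same 206, 80% power and 10% loss, but assumes 62% adherence and names 3.8 points as the change to be detected.

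**The concern.** Sections 3 and 3.1 follow one another and disagree on whether the trial has one primary hypothesis or two. Someone reporting an 8-month result could cite 3.1 to call it primary or section 3 to call it secondary. If both were treated as primary, each tested at 0.05 with either sufficient for a claim, the overall type I error would exceed the 5% for which the trial is sized.

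The planning effect is the figure from which the sample size follows, and the reason 9.2 gives for it does not produce it. A reader of 5.3 may also conclude that the intention-to-treat contrast is powered for the minimal clinically important difference itself. It is powered for a smaller one, and that affects how an observed difference would be read.

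**Working it through.** **Inputs.** Effect 0.42 = 3.8 points, planning effect 0.26, test-retest r = 0.78, two-sided alpha 0.05, power 80%, drop-out 10%, adherence about 70% (all 9.2); adherence 62% (5.3); 1:1 allocation (5.6).

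**1. The plan's own sample size.** The ANCOVA residual SD, in SD units, is sqrt(1 - 0.78²) = 0.6258.

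- Normal approximation: n per arm = 2 x (1.960 + 0.842)² x 0.3916 / 0.26² = 90.9, so 91 per arm and 182 in total.
- Noncentral t with 92 per arm: df = 184 - 3 = 181, noncentrality = (0.26 / 0.6258) x sqrt(92/2) = 2.82, power 80.0%. The stated 184 reproduces.
- Drop-out: 184 / 0.9 = 204.4, so 205; 206 in equal groups is consistent.

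**2. Where 0.26 comes from.** Assume non-adherers gain nothing, so that the diluted effect is the full effect times adherence.

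| Full effect | Adherence | Diluted effect |
|---|---|---|
| 0.42 | 62% | 0.260 |
| 0.42 | 70% | 0.294 |
| 0.46 (observational study) | 62% | 0.285 |
| 0.46 | 70% | 0.322 |

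Only the first row gives 0.26; conversely, 0.26 / 0.42 = 0.619.

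**3. What the mismatch does to power (noncentral t).** With 184 analysed, power is 80.0% at 0.26 and 88.7% at 0.294. The discrepancy is on the conservative side.

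**4. What 3.8 points means.** The implied SD is 3.8 / 0.42 = 9.05 points. The intention-to-treat difference the trial is sized for is 0.26 x 9.05 = 2.35 points. Were 3.8 points (0.42) the between-arm target, 72 analysed would give 80% power.

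**5. Error rate if both 3.1 objectives were primary.** The SDMT correlation between 4 and 8 months is not given, so take r = 0.78 between any two visits. The correlation of the two baseline-adjusted tests is then (0.78 - 0.78²) / (1 - 0.78²) = 0.438. The chance that at least one of two null tests is significant at 0.05, from the bivariate normal distribution, is:

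| Assumed 4-to-8-month r | Family-wise error |
|---|---|
| 0.90 | 8.1% |
| 0.78 | 9.2% |
| 0.70 | 9.6% |
| Tests independent | 1 - 0.95² = 9.75% |

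**6. Cost of splitting alpha.** At 0.025 per test, 4-month power with 184 falls to 71.1%. Restoring 80% needs 224 analysed; 224 / 0.9 = 248.9, or 250 in equal groups.

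**The case against.** The strongest reply is that the operative text is clear. Section 3, 9.2, 9.4 and the summary's analysis entry all point to one primary test at 4 months, and 3.1 is the outlier. The summary's Primary Outcome(s) entry is weak support for a second primary test, because it also lists the supplementary cognitive measures. Nothing in the protocol proposes two tests at 0.05 each, and a multiplicity rule may sit in an analysis plan that is not shown. This stands as far as the error rate goes: 9.2% is what 3.1 would imply if it governed, not a property of the analysis in 9.4. It does not remove the conflict, since an analysis plan can set a testing order but cannot make sections 3 and 3.1 agree.

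On adherence, 62% is disclosed in 5.3, planning below a cited figure is prudent, and 9.2 writes no formula. It is fair that 62% as the origin of 0.26 is an inference. A rival route, 0.42 x 0.70 x 0.90 = 0.265, comes close but would count drop-out twice, because 9.2 already inflates 184 to 206 for it. Section 9.2 does say that 0.26 accounts for the roughly 70%, and that figure does not yield it. The mention of 62% beside 3.8 points hints at dilution without stating the diluted target.

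A further fair point concerns testing 8 months as a confirmatory hypothesis. Both arms have CPAP by then, the contrast may be smaller, and 9.2 does not size it. Purely as an illustration, assumed effects of 0.13 to 0.20 with the same r would give about 29% to 58% power with 184.

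**Conclusion.** Both parts hold.

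The rank of the 8-month hypothesis is contradictory. The weight of the text favours a single primary test at 4 months, so family-wise error rises (to about 9.2%, assuming equal correlation between visits) only if 3.1 is taken as governing. What is at stake is the claim an 8-month result may support.

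The reason 9.2 gives for 0.26 does not produce it. The figure matches the 62% of 5.3, assuming no benefit in non-adherers, and the between-arm target is about 2.35 points rather than 3.8. This is an error of justification and presentation. It is conservative, and 184 analysed and 206 recruited stand. The protocol should be corrected, but the design is not in danger.

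**What to change.** 1. Move objective 2 from 3.1 to 3.2 and bring the summary's Primary Outcome(s) entry into line with section 3 and 9.4. Section 4.2 defines the primary outcome without a visit; adding 4 months there would complete the alignment.
2. If the sponsor wants the 8-month comparison to be confirmatory, test it at 0.05 in fixed sequence, only after a significant 4-month result. Do not split alpha. State the effect expected at 8 months and the power for it, since 9.2 covers only the 4-month test.
3. In 9.2, write out the dilution step (0.42 x 0.62 = 0.26, no benefit assumed in non-adherers), if the sponsor confirms that this is how 0.26 was obtained. Explain why 62% is used when the cited study gives about 70%, and state the intention-to-treat target of about 2.35 points.
4. In 5.3, say that 3.8 points is the effect before dilution and 2.35 points the between-arm difference for which the trial is powered.
5. Keep the sample size at 206.

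The cost is protocol wording, with no added participants and no loss of 4-month power. The price is that no confirmatory 8-month claim is possible if the 4-month test fails, or none at all if objective 2 becomes secondary.
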